# Statistical Analysis Plan (SAP) for Non-Interventional Studies (NIS) BI Study Number 1160-0304

Page 18 of 27

Statistical Analysis Plan (SAP) for Non-Interventional Studies (NIS) BI Study Number 1160-0304

Page 19 of 27

#### 7.1.3 Covariates

Patients recruited will be evaluated for covariates at the visit of baseline. Potential confounders include demographics (age, gender, race, and educational level), VASc score, HASBLED score, comorbidities, concomitant therapies, dose of dabigatran, and renal function.

Statistical methods will be performed to test the difference of covariates between the study group at the visit of baseline (please referred to section 10. data analysis). If any significant difference occurred, linear regression will be conducted to model the relationship between dependent variable and all explanatory variables.

As for linear regression model, the primary endpoint (MMAS-8 score at 12 months) will be considered as dependent variable, and all covariates listed above including study group variable will be considered as explanatory variable.

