## Statistical Analysis Plan (SAP) for Non-Interventional Studies (NIS) BI Study Number 1160-0304

Page 21 of 27

while the other six items are counted as 1 point of each. A higher score corresponds to a greater risk of stroke. The VASc score is calculated according to Table 2.

If any of the clinical characteristic shown in Table 2 is missing or not known, the CHA2DS2-VASc score will be considered as a missing value during data analysis.

Table 2 Acronym VASc and the score

Letter	Clinical Characteristic	Score
V	Vascular disease (prior myocardial infarction, peripheral artery disease, or aortic plaque)	1
A	Age 65 – 74 years	1
Sc	Sex category (i.e., female sex)	1

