#### 7.1.3.5 HAS-BLED score

HAS-BLED is a scoring system developed to assess 1-year risk of major bleeding in patients with AF. The HAS-BLED score is composed of seven items with a maximum score of 9. Among all the items, 2 of them will be scored with 1 or 2 points depending on the number of corresponding description, including "abnormal renal and liver function" and "drugs or alcohol", while the other five items are counted as 1 point of each. A higher score corresponds to a greater risk of bleeding, and a score of  $\geq$  3 points indicates "high risk". The HAS-BLED score will be calculated according to Table 3.

If labile INRs in current study is not known, we will consider it as no labile INRs in calculating HAS-BLED score under the premise of no statistical significant difference in the distribution of labile INRs between two study group.

Besides labile INRs, if any of the clinical characteristic shown in Table 3 is missing or not known, the HAS-BLED score will be considered as a missing value during data analysis.

Table 3 Clinical characteristics composing the HAS-BLED score

Letter	Clinical Characteristic	Score
Н	Hypertension 	1
A	Abnormal renal function  and abnormal liver function  (1 point each)	1 or 2
S	Stroke 	1
В	Bleeding 	1

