#### 9.2 Handling of Missing Values

No imputation method will be performed to estimate the missing values for all the study variables.

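### If triggered, the adjusted model of 12-month MMAS-8 is complete-case: one unknown covariate or risk-score item (labile INR conditionally excepted) removes the patient

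*SAP*

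**What the plan says.** SAP 7.1.3 names the covariates: "Potential confounders include demographics (age, gender, race, and educational level), VASc score, HASBLED score, comorbidities, concomitant therapies, dose of dabigatran, and renal function". They are tested between arms at baseline, and "If any significant difference occurred, linear regression will be conducted to model the relationship between dependent variable and all explanatory variables". The outcome of that regression is the 12-month MMAS-8 score. On the explanatory side the SAP says that "all covariates listed above including study group variable will be considered as explanatory variable". There is no selection step.

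Three rules decide what happens to unknown values:

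- SAP 7.1.3.4: if any item is unknown, the "VASc score will be considered as a missing value during data analysis".
- SAP 7.1.3.5: if any item apart from labile INR "is missing or not known, the HAS-BLED score will be considered as a missing value during data analysis". Unknown labile INR is scored as absent, provided its distribution does not differ significantly between arms.
- SAP 9.2: "No imputation method will be performed to estimate the missing values for all the study variables".

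Baseline data come from charts and are recorded only where available (SAP 6.2.3.1). No assessments are added to routine practice (SAP 8), and Protocol 9.9 names lack of data as a possible limitation. For the unadjusted analyses, the only missing-data exclusion is for a missing MMAS-8 value at the visit concerned (Protocol 9.7.1, SAP 10.1).

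**The concern.** The SAP does not use the term complete-case, but a linear regression fitted with no imputation can use only patients with every explanatory variable known. A patient whose arm and 12-month MMAS-8 are both known is lost if one chart item was not recorded. The model's purpose is to show whether a baseline imbalance explains the arm difference. If the set of patients changes along with the adjustment, a shift between the unadjusted and adjusted mean difference cannot be put down to the imbalance. Precision is also lost, in the only adjusted arm comparison in the visible text.

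**Working it through.** **1. Starting number.** Protocol 9.5 goes from 1,200 enrolled and 20% drop-out to 1,000 completers. This does not reproduce: 1,200 × 0.80 = 960, and 1,000 / 0.80 = 1,250. The figure of 1,200 is 1,000 × 1.20, and 1,000 of 1,200 corresponds to drop-out of 1 − 1,000/1,200 = 16.7%. That is a separate matter. Here it only sets the base at 960 to 1,000 patients with a 12-month score.

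**2. Who is dropped.** Read together, the rules remove a patient if any of these is unknown: a covariate on the list, a VASc item, or a HAS-BLED item other than labile INR. Baseline data outside the list and both scores, such as AF type, remove nobody.

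**3. Where the loss comes from.** Count the score items that a chart could leave unknown.

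- Nine also enter as covariates: heart failure, hypertension, diabetes, stroke/TIA/thromboembolism, vascular disease, renal, liver, bleeding, and antiplatelet/NSAID use.
- Two enter only through HAS-BLED: alcohol and systolic pressure above 160 mmHg. Table 1 of the SAP and the visit lists show no blood pressure entry, so the second could be unknown for many patients if the CRF does not capture it.

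Assume each item is unknown independently at rate m (an assumption; the documents give no rate). The share deleted is 1 − (1 − m)^k, with k = 11 with the scores in the model and k = 9 without them. Per 1,000 patients:

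| m | deleted, k = 11 | deleted, k = 9 | added by the scores |
|---|---|---|---|
| 0.5% | 54 | 44 | 10 |
| 1% | 105 | 86 | 18 |
| 2% | 199 | 166 | 33 |
| 5% | 431 | 370 | 61 |

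(Differences are taken before rounding.) Race, education, dose and creatinine clearance are not counted and could only add to the loss.

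**4. How redundant the scores are.** Under age 75, every VASc item comes from age, gender or a listed comorbidity. For HAS-BLED, six of the nine points (renal, liver, stroke, bleeding, age, drugs) have a counterpart among the covariates, although the renal comorbidity is wider because it includes eGFR below 60. Alcohol, labile INR and the pressure cut have none. In a simulation with assumed, independent prevalences (for example hypertension 60%, diabetes 25%, women 40%, alcohol 10%), the other covariates explained about 94% of the variance of VASc and about 70% of that of HAS-BLED. The variance inflation factors, with the other score also in the model, were about 23 and 5.

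**5. Precision.** With a fraction d deleted and residual variance and arm balance unchanged, the standard error of the arm effect is multiplied by 1/√(1 − d).

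| d | left of 960 | left of 1,000 | factor |
|---|---|---|---|
| 10% | 864 | 900 | 1.054 |
| 20% | 768 | 800 | 1.118 |
| 30% | 672 | 700 | 1.195 |

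Under step 3, these losses correspond to m = 1 − (1 − d)^(1/11), or about 1.0%, 2.0% and 3.2% unknown per item.

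**The case against.** The strongest reply is that this is a conditional, supportive model, that the primary test does not depend on it, and that the extent of missing data will be visible because SAP 10 reports missing counts. All of that is true. The condition is not remote, however. Under randomisation, with independent tests at 0.05, the chance of at least one significant baseline difference is 1 − 0.95^10 = 40% for 10 tests and 1 − 0.95^20 = 64% for 20. Reporting the counts does not bring patients back into the model.

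Several stronger readings are tempting and are not supported:

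- *Any unknown baseline item removes the patient.* Labile INR is conditionally exempt, and items outside the model do not matter. Eligibility also forces some information to be known, such as creatinine clearance and active bleeding.
- *The two scores cause the loss, so removing them cures it.* An unknown comorbidity removes the patient through its own term. The SAP lists antiplatelet/NSAID use as a concomitant therapy in 7.1.3.3, but the baseline list in 7.1.3.1 names only AF and stroke-prevention therapies. If the drugs item is not in the model, k without the scores is 8 and the scores add 1.4 to 9.5 percentage points over m = 0.5% to 5%. That is still the smaller part.
- *Both scores are superfluous.* That is close to true for VASc but only partly true for HAS-BLED. The SAP also does not say whether comorbidities enter one by one or as a count, and the visible Table 2 shows only three VASc rows, so the heart failure, hypertension and diabetes items are inferred from the score's full name.
- *The primary result is compromised.* It is a test on the proportion scoring 8. The regression uses the score itself, so its proper counterpart is the mean-score comparison, which may be run as a Wilcoxon test.
- *The adjusted estimate is biased, or a stated power is lost.* Deletion that depends only on covariates need not bias a linear model with a common arm effect, and the plan states no power.

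**Conclusion.** The point holds within limits. If SAP 7.1.3 is triggered, its regression compares the arms in a smaller and better-documented subset than the unadjusted mean-score comparison, so the two cannot be read as the same comparison with and without adjustment. The primary Chi-square/Fisher test stands as planned. The size is illustrative: about 5% to 43% of patients deleted at 0.5% to 5% unknown per item, of which the scores account for about 1 to 6 percentage points, and a standard error 5% to 20% larger if 10% to 30% are lost. These figures rest on assumed missingness rates and independence between items. The exception is the systolic pressure item: if the CRF does not record it, HAS-BLED alone could remove many patients.

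**What to change.** Amend SAP 9.2 for baseline covariates in this model only. Replace a missing continuous covariate by the overall mean across both arms and add a missing indicator; give a missing categorical covariate an 'unknown' level. State that only values dated at or before randomisation are used. The method relies on this, and SAP 6.2.3.1 lists randomisation ahead of several baseline collections, which does not prove the timing but leaves it open. Protocol 9.7.3 already allows imputation case by case if the SAP describes it.

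In SAP 7.1.3, drop the VASc score and replace HAS-BLED by its components, adding the alcoholic status already collected and, if the CRF captures it, the systolic pressure item. Say whether comorbidities enter separately and which therapies are included.

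Every patient with a 12-month MMAS-8 then stays in, and the adjusted and unadjusted mean-score comparisons have the same N. The cost is SAP wording, minor programming and some extra indicator terms, small against roughly 960 to 1,000 patients. No new data are needed.

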#### 7.1.3.1 Baseline characteristics

- Demographics (date of birth, gender, race, educational level, height, weight, and alcoholic status [defined as  $\geq 8$  units of consumption per week])
- AF-related medical histories (date of AF diagnosis and type of AF [paroxysmal, persistent or permanent])
- Kidney function (CrCl and eGFR)

Value of serum creatinine within the allowed window (i.e., the latest data before baseline & data within  $\pm$  6 weeks for follow-up visits) will be collected from medical chart to calculate the CrCl value by Cockcroft-Gault formula as below.

When serum creatinine is measured in mg/dL, the value is multiplied by a constant of 0.85 if the patient is female.

$$eC_{Cr} = rac{(140 ext{ - Age}) imes ext{Mass (in kilograms)} imes [0.85 \, if \, Female]}{72 imes ext{Serum Creatinine (in mg/dL)}}$$

(1) When serum creatinine is measured in µmol/L, constant is 1.23 for male and 1.04 for female.

$$eC_{Cr} = \frac{(140 ext{ - Age}) \, imes \, ext{Mass (in kilograms)} \, imes \, Constant}{ ext{Serum Creatinine (in $\mu$mol/L)}}$$

- VASc score (Section 7.1.3.4)
- HAS-BLED score (Section 7.1.3.5)
- Comorbidities (Section 7.1.3.2)
- Concomitant therapies for AF or stroke prevention: Generic name or name of the therapy

#### 7.1.3.2 Comorbidities

Comorbidities include hypertension, diabetes, congestive heart failure, vascular disease (myocardial infarction, peripheral artery disease, and complex aortic plaque), ischemic heart disease, left ventricular dysfunction, stroke, transient ischemic attack, thromboembolism,

## Statistical Analysis Plan (SAP) for Non-Interventional Studies (NIS) BI Study Number 1160-0304

Page 20 of 27

abnormal kidney function (chronic dialysis, renal transplantation, serum creatinine  $\geq$  200 µmol/L, or eGFR < 60 mL/min/1.73 m²), abnormal liver function (chronic hepatic disease [e.g., cirrhosis] or biochemical evidence of significant hepatic derangement [e.g., bilirubin > 2 × upper limit of normal, in association with AST/ALT/ALP > 3 × upper limit normal]), major bleeding, and predisposition to bleeding/anemia.

At baseline, comorbidities will be recorded as follows according to the medical records:

- Currently ongoing diseases: Hypertension; diabetes, congestive heart failure, left ventricular dysfunction, abnormal kidney function (chronic dialysis, renal transplantation, serum creatinine ≥ 200 μmol/L, or eGFR < 60 mL/min/1.73 m²), abnormal liver function (chronic hepatic disease [e.g., cirrhosis] or biochemical evidence of significant hepatic derangement [e.g., bilirubin > 2 × upper limit of normal, in association with AST/ALT/ALP > 3 × upper limit normal]), major bleeding, and predisposition to bleeding/anemia.
- Prior events: Vascular disease (myocardial infarction, peripheral artery disease, and complex aortic plaque) ischemic heart disease, stroke, transient ischemic attack, thromboembolism

At follow-up visits, only the current and newly onset of comorbidities since the last visit (regardless of its condition, resolved or unresolved) should be recorded on the CRF.

#### 7.1.3.3 Concomitant therapy

The study will collect two types of concomitant therapies, including (1) therapies related to the calculation of HAS-BLED score and (2) therapies for AF or stroke prevention. These therapies will be collected according to the plan as below:

- (1) Therapies related to HAS-BLED score include chronic dialysis or renal transplant due to abnormal renal function & medication usage predisposing to bleeding (antiplatelet agents or NSAIDs).
- Baseline: Chronic dialysis or renal transplant prior to baseline will be collected, while medication usage predisposing to bleeding within 1 month prior to baseline will be collected.
- Follow-up visits at every 3 months: Used during the interval of visits will be collected
- (2) Therapies for AF or stroke prevention:
- Baseline: Used within 1 month prior to the enrolment will be collected at baseline.
- Follow-up visits at every 3 months: Changes in concomitant therapies will be collected.

## 7.1.3.4 VASc score

The VASc score is a clinical prediction rule for estimating the risk of stroke in patients with non-rheumatic AF. The VASc score is composed of eight items with a maximum score of 9. Among all the items, two of them have extra weight of 2 points, including "age 75 and above" and "stroke, transient ischemic attack, and thromboembolism";

## Statistical Analysis Plan (SAP) for Non-Interventional Studies (NIS) BI Study Number 1160-0304

Page 21 of 27

while the other six items are counted as 1 point of each. A higher score corresponds to a greater risk of stroke. The VASc score is calculated according to Table 2.

If any of the clinical characteristic shown in Table 2 is missing or not known, the CHA2DS2-VASc score will be considered as a missing value during data analysis.

Table 2 Acronym VASc and the score

Letter	Clinical Characteristic	Score
V	Vascular disease (prior myocardial infarction, peripheral artery disease, or aortic plaque)	1
A	Age 65 – 74 years	1
Sc	Sex category (i.e., female sex)	1

#### 7.1.3.5 HAS-BLED score

HAS-BLED is a scoring system developed to assess 1-year risk of major bleeding in patients with AF. The HAS-BLED score is composed of seven items with a maximum score of 9. Among all the items, 2 of them will be scored with 1 or 2 points depending on the number of corresponding description, including "abnormal renal and liver function" and "drugs or alcohol", while the other five items are counted as 1 point of each. A higher score corresponds to a greater risk of bleeding, and a score of  $\geq$  3 points indicates "high risk". The HAS-BLED score will be calculated according to Table 3.

If labile INRs in current study is not known, we will consider it as no labile INRs in calculating HAS-BLED score under the premise of no statistical significant difference in the distribution of labile INRs between two study group.

Besides labile INRs, if any of the clinical characteristic shown in Table 3 is missing or not known, the HAS-BLED score will be considered as a missing value during data analysis.

Table 3 Clinical characteristics composing the HAS-BLED score

Letter	Clinical Characteristic	Score
Н	Hypertension 	1
A	Abnormal renal function  and abnormal liver function  (1 point each)	1 or 2
S	Stroke 	1
В	Bleeding 	1

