#### 6.2.3 STUDY VISITS

The collection of patient data will be managed in line with routine clinical practice in an outpatient manner, which will have follow-ups at approximately every 3 months in Taiwan. Information on variables of interest will be collected at inclusion (baseline visit) and captured during the follow-up period at 3, 6, 9, and 12 months (time window:  $\pm$  6 weeks) until completion of the study.

Data will be collected and recorded on the CRF according to Table 1 which lists all of the data of interests with an "X" to show the time points when they are collected. Data will be collected after the patient has consented to participate in the study. Once the patient has signed the informed consent form, the patient is considered to be enrolled in the study and patient details should be recorded on the enrolment log.

Table 1 Data collection schedule

Event	Screening/Baseline	Follow-up			
Visit	1	2	3	4	5
Month	0	3	6	9	12
Week	0	12	24	36	48
Allowed window	==		± 6 v	veeks	
Informed consent	X	·			
Inclusion/exclusion	X				
Randomization	X				
Demographics 	X	W/A	W/A	W/A	W/A
AF-related medical histories 	X				
Comorbidities	$X^3$	$X^4$	$X^4$	$X^4$	$X^4$
Serum creatinine (for CrCl) and eGFR 	X	X	X	X	X
VASc score	X	X	X	X	X
HAS-BLED score	X	X	X	X	X
Lab data for HAS-BLED 	X	X	X	X	X
Concomitant therapies for HAS-BLED 	X	X	X	X	X
Education (experimental group)	X	X	X	X	
Dabigatran treatment	X	X	X	X	X
Concomitant therapies for AF or stroke 	X	X	X	X	X
MMAS-8 score		X	X	X	X
Stroke and thromboembolic events 					→
Bleeding-related events 					→
Safety reporting 					$\rightarrow$

- Demographics include date of birth, gender, race, education level, height, weight, and alcoholic status (defined as ≥ 8 units [1 unit = approximately 355-mL beer, 150-mL wine, 20-mL Kaoliang] of consumption per week). Follow-up visits will only collect weight (W) and alcoholic status (A).
- 2. Include date of AF diagnosis and type of AF (paroxysmal, persistent or permanent).

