#### 6.2.3.1 Screening/Baseline (Visit 1)

The following procedures will be performed at the baseline visit. Data will be collected from the medical charts and recorded on the CRF when they are available.

- Collect signed informed consent form. A copy of the signed consent should be given to the patient.
- Assess the eligibility according to the inclusion/exclusion criteria and record the date of inclusion
- Randomize the eligible patients into one of the study groups (standard of care OR standard of care with advanced educational intervention)
- Collect demographic data (date of birth, gender, race, education level, height, weight, and alcoholic status [defined as  $\geq 8$  units of consumption per week])
- Record AF-related medical histories
- Record the following comorbidities:
  - Currently ongoing diseases: Hypertension, diabetes, congestive heart failure, left ventricular dysfunction, abnormal kidney function (chronic dialysis, renal transplantation, serum creatinine ≥ 200 μmol/L, or eGFR < 60 mL/min/1.73 m²), abnormal liver function (chronic hepatic disease [e.g., cirrhosis] or biochemical evidence of significant hepatic derangement [e.g., bilirubin > 2 × upper limit of normal, in association with AST/ALT/ALP > 3 × upper limit normal]), major bleeding, and predisposition to bleeding/anemia.
  - Prior events: Vascular disease (myocardial infarction, peripheral artery disease, and complex aortic plaque), ischemic heart disease, stroke, transient ischemic attack, and thromboembolism
- Collect the latest results of serum creatinine (will be used to calculate CrCl by Cockcroft-Gault formula) and eGFR prior to the baseline
- To acquire HAS-BLED score:
  - Record the latest results of bilirubin, AST, ALT, ALP, INR, and PT prior to the baseline
  - Record if the subject is receiving chronic dialysis or had undergone renal transplant due to abnormal renal function prior to the baseline; and medication usage predisposing to bleeding (antiplatelet agents or NSAIDs) within 1 month prior to the baseline

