#### 6.2.3.2 Month $3 \pm 6$ weeks (Visit 2)

The following procedures will be performed at 3 months after the baseline. Data will be collected from the medical charts and recorded on the CRF when they are available.

- Record the weight and alcoholic status (defined as  $\geq 8$  units of consumption per week)
- Record the active or newly onset of comorbidities since the baseline (during baseline to Month 3). Comorbidities include hypertension, diabetes, congestive heart failure, vascular disease (myocardial infarction, peripheral artery disease, and complex aortic plaque), ischemic heart disease, left ventricular dysfunction, stroke, transient ischemic attack, thromboembolism, abnormal kidney function (chronic dialysis, renal transplantation, serum creatinine ≥ 200 μmol/L, or eGFR < 60 mL/min/1.73 m²), abnormal liver function (chronic hepatic disease [e.g., cirrhosis] or biochemical evidence of significant hepatic derangement [e.g., bilirubin > 2 × upper limit of normal, in association with AST/ALT/ALP > 3 × upper limit normal]), major bleeding, and predisposition to bleeding/anemia.
- Collect the results of serum creatinine (will be used to calculate CrCl by Cockcroft-Gault formula) and eGFR if available in medical record. Only the values within the allowed window and closest to 3 months will be collected.
- To acquire HAS-BLED score:
  - Record the results of bilirubin, AST, ALT, ALP, INR, and PT if available in medical record. Only the values within the allowed window and closest to 3 months will be collected.
  - Record if the subject is receiving chronic dialysis or have undergone renal transplant due to abnormal renal function, and medication usage predisposing to bleeding (antiplatelet agents or NSAIDs) during baseline to 3 months

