## Statistical Analysis Plan (SAP) for Non-Interventional Studies (NIS) BI Study Number 1160-0304

Page 22 of 27

L	Labile INRs 	1
Е	Elderly, age > 65 years	1
D	Drugs or alcohol (1 point each) 	1 or 2

- 1. Hypertension should be uncontrolled, with systolic blood pressure > 160 mmHg.
- 2. Abnormal kidney function is classified as a presence of chronic dialysis, renal transplantation, or serum creatinine  $\geq 200 \ \mu mol/L$ .
- 3. Abnormal liver function is defined as the chronic hepatic disease (e.g., cirrhosis) or biochemical evidence of significant hepatic derangement (e.g., bilirubin > 2 × upper limit of normal, in association with AST/ALT/ALP > 3 × upper limit normal, and so forth.)
- 4. Previous history, particularly lacunar.
- 5. Bleeding history, such as prior major bleeding or predisposition to bleeding (e.g., anemia).
- 6. Labile INR (e.g., therapeutic time in range < 60%).
- 7. Drugs are medication usage predisposing to bleeding (e.g. antiplatelet agents or NSAIDs). Ethanol abuse is classified as  $\geq 8$  units of alcoholic consumption per week.

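### HAS-BLED is voided by one unknown item, but its hypertension item has no scheduled source, so some patients may drop from the conditional adjusted regression and the HAS-BLED summaries

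*SAP*

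**What the plan says.** **Scoring rule.** SAP 7.1.3.5 exempts labile INR. For every other item, one unknown characteristic voids the score: it "is missing or not known, the HAS-BLED score will be considered as a missing value during data analysis". Note 1 to Table 3 defines the H item: "Hypertension should be uncontrolled, with systolic blood pressure > 160 mmHg".

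**Data collected.** Table 1 (SAP 6.2.3) has no row for blood pressure. Its footnote on patient measurements reads "Demographics include date of birth, gender, race, education level, height, weight, and alcoholic status". Hypertension is recorded as a comorbidity, without a threshold or control status. For liver tests, the baseline visit says "Record the latest results of bilirubin, AST, ALT, ALP, INR, and PT prior to the baseline", under a general proviso that chart data are entered when available. The follow-up visits say "Record the results of bilirubin, AST, ALT, ALP, INR, and PT if available in medical record". SAP 8 allows no tests beyond routine care.

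**Labile INR.** An unknown value is taken as not labile, but only "under the premise of no statistical significant difference in the distribution of labile INRs between two study group".

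**Use of the score.** SAP 7.1.3 names HAS-BLED among the baseline covariates. If any baseline covariate differs significantly between groups, a linear regression of the month-12 MMAS-8 score is run, in which "all covariates listed above including study group variable will be considered as explanatory variable". SAP 9.2 adds: "No imputation method will be performed to estimate the missing values for all the study variables". The primary test in SAP 10.1 is an unadjusted Chi-square or Fisher test that leaves out only patients with no month-12 MMAS-8 value.

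**The concern.** The plan makes the score all-or-nothing without listing a data source for one of its items. The list of what to record in order to obtain HAS-BLED covers laboratory results, dialysis or transplant, and drugs that predispose to bleeding. It does not cover pressure. A patient whose chart says hypertension cannot be placed above or below 160 mmHg from the listed data.

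Under the no-imputation rule, a patient with a void score is deleted from any model that contains HAS-BLED. The loss would probably not be random: it falls on patients with hypertension and on those tested less. The adjusted estimate, which is meant to address a baseline imbalance, would then describe a different set of patients from the primary test. HAS-BLED is also recorded at all five visits, so the same rule thins its descriptive summaries.

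**Working it through.** **1. Base for the counts.** The documents give 1,200 enrolled, 20% drop-out and 1,000 completers. These do not agree: 1,200 × (1 − 0.20) = 960, and 1,000 completers would need 1,000 / 0.80 = 1,250 enrolled. Both bases are shown below; the percentages do not depend on the choice.

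**2. Can each item be scored from the listed baseline data?**

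| Item | Table 3 needs | Listed data | Result |
|---|---|---|---|
| H | systolic > 160 mmHg | hypertension as comorbidity | 0 if no hypertension; otherwise undetermined |
| A, renal | dialysis, transplant or creatinine ≥ 200 µmol/L | all three | scorable if creatinine is in the chart |
| A, liver | chronic hepatic disease or biochemical evidence | comorbidity and latest labs | diagnosis gives the point; with neither, the plan does not say |
| S, B, E, D | history, age, drugs, alcohol | recorded | scorable |
| L | labile INR, e.g. time in range < 60% | latest INR before baseline; later, the value closest to each visit | no time in range available |

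**3. The labile-INR condition.** Unknown becomes not labile only if labile INR does not differ significantly between groups. Where the item is unknown there is nothing to test, and no fallback is given if a test is significant. Filling in a fixed value also sits badly with SAP 9.2, which excludes imputation for every study variable.

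**4. Loss from the regression.** The documents give no missingness rate, so this step is an assumption. Let a be the share with H unknown and b the share with the liver item unknown, taken as independent. The share retained is (1 − a)(1 − b). With a total share m missing, the confidence interval for the group effect widens by about 1/√(1 − m).

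| a / b | Retained | Lost | Left of 960 / 1,000 | Interval wider by |
|---|---|---|---|---|
| 5% / 5% | 0.95 × 0.95 = 0.9025 | about 10% | 866 / 902 | 1/0.95, about 5% |
| 20% / 20% | 0.80 × 0.80 = 0.64 | 36% | 614 / 640 | 1/0.80 = 25% |
| 50% / 40% | 0.50 × 0.60 = 0.30 | 70% | 288 / 300 | 1/√0.30, about 83% |

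**5. Who is lost.** If patients without hypertension are scored H = 0, then a is the share with recorded hypertension multiplied by the share of those with no pressure reading. Neither factor is in the documents. In the limit where no pressure is captured, every patient with hypertension drops out. Hypertension, itself a covariate in the model, then no longer varies.

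**6. How often the regression would run.** SAP 7.1.3 names ten covariates or covariate groups if comorbidities count as one, and 9 + 13 = 22 if the 13 comorbidities are tested singly. Under randomisation alone, with independent tests at 0.05, the chance of at least one significant result is 1 − 0.95^10 = 40% or 1 − 0.95^22 = 68%. The condition is not remote.

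**The case against.** The strongest reply is that little depends on this. The primary test is unadjusted and does not use HAS-BLED. The regression is contingent and supplementary. That stands, and it limits the reach of the point.

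It can also be said that an absent input is not an unknown item. A patient without hypertension can be scored H = 0. Chronic liver disease is a recorded comorbidity and earns the point without labs. Baseline labs have no look-back limit, and the wording that restricts labs to those found in the record belongs to the follow-up visits, whereas the regression uses baseline values. HAS-BLED is itself scheduled at every visit. The CRF is not among the documents, and protocol 9.8 refers to chart records and physical examination on the CRF, so pressure may in fact be captured. All of this stands as a reason not to claim a large loss. It does not supply a rule for patients with recorded hypertension, or for patients with neither liver tests nor a liver diagnosis.

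On labile INR, a specific scoring convention can reasonably override the general statement in SAP 9.2. That weakens the conflict but does not give the between-group test any data. The protocol abstract mentions a modified HAS-BLED for newly initiated patients, which might have settled this, but neither protocol 9.3.3.5 nor SAP 7.1.3.5 defines one.

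A reader might infer that HAS-BLED will be missing for most or all patients, or that the primary analysis runs on a selected subset. The documents support neither. They give no missingness rate, and SAP 10.1 keeps these patients in the primary test.

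**Conclusion.** The point holds, with limited reach. Followed as written, the SAP voids HAS-BLED whenever H cannot be determined, lists no data that determine H in a patient with hypertension, and allows no imputation. An unknown and probably non-random share would drop out of the conditional regression of the month-12 MMAS-8 score and out of the HAS-BLED summaries. The primary Chi-square or Fisher test is unaffected. The labile-INR condition cannot be applied where it is needed.

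The size is not in the documents. The losses of about 10% (5%/5%) and 36% (20%/20%) are illustrations that assume the two items are unknown independently; the 70% case is an upper illustration. The conclusion also assumes that the CRF follows the visit lists. If it already captures systolic pressure, the H part shrinks to patients without a reading in the chart.

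**What to change.** 1. Add systolic pressure from the routine chart (reading closest to the visit) to Table 1 and the visit lists. Score H = 0 where no hypertension is recorded.
2. Score the liver and renal items from the recorded comorbidity plus labs when present, and report how many patients had no labs. For the renal item, use the dialysis, transplant and creatinine entries: the comorbidity definition in SAP 7.1.3.2 also counts eGFR < 60, which note 2 to Table 3 does not.
3. Score labile INR as 0 for all patients without INR monitoring, delete the between-group test condition, and state in SAP 9.2 that this is a scoring convention outside the ban on imputation.
4. In the adjusted regression, enter the recorded HAS-BLED components, or use a missing indicator for the baseline score, so that no randomised patient with a month-12 score is dropped because HAS-BLED is missing. An indicator is reasonable here because the covariate predates allocation, so its missingness should not depend on group. It too needs a line in SAP 9.2.

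The cost is one CRF field taken from existing charts, with no new procedure, plus SAP wording. The downside is that some items scored 0 will be misclassified, which is why the number handled this way should be reported.
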